2.9.3 Other safety data

2.9.3.1 Vital signs

Analysis of the vital sign measurements using summary statistics for the change from Baseline for each post-baseline visit will be performed. These descriptive summaries will be presented by vital sign and treatment group. Change from Baseline will only be summarized for patients with both Baseline and post-baseline values. Vital signs included are: weight (kg), BMI = weight (kg) / (height at visit 1 (meters))², waist circumference (cm), hip circumference (cm), waist to hip ratio = waist, circumference (cm)/ hip circumference (cm), sitting pulse (bpm), systolic and diastolic blood pressure (mmHg).

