ability to lose weight under these medications (weight gain is a well-known side effect of insulin and sulfonylurea agents/analogues). Patients with type 2 diabetes receiving other medications, such as DPP4 inhibitors, are allowed to participate in the study, as lifestyle intervention is the guideline-recommended basic therapy for any patient with type 2 diabetes (NVL Therapie des Type-2-Diabetes), and offers benefit for them, which outweighs the potential small risk of hypoglycemia or ketoacidosis in the case of metformin. The treating family physicians of the patients participating in the lifestyle intervention will be notified about the participation in the lifestyle intervention, so they can adequately monitor them and adjust their antidiabetic or antihypertensive medication.

Based on the current knowledge no interactions with negative consequences between Secukinumab therapy and lifestyle intervention can be expected. On the contrary, it is the goal of this study to assess potential positive effects of the combined application. The risk will be further minimized by close clinical and laboratory monitoring of participating patients at all study visit.

The additional risks of participating in the biomarker sub-study are those of blood sampling. Blood sampling will occur at time points where standard blood sampling is scheduled as well, and will not require additional venipuncture. Participation in the sub-study does not negatively affect the overall risk-benefit ratio for participation in the study.

4 Population

The study is conducted in Germany and the study population consists of a representative group of male and female patients (≥ 18 years old) with moderate to severe plaque-type psoriasis and concomitant metabolic syndrome according to International Diabetes Federation (IDF), American Heart Association (AHA), and National Heart, Lung and Blood Institute (NHLBI) consensus definition from 2009 (Alberti et al., 2009). The goal is to randomize a total of approximately 760 patients in approximately 100 sites in Germany. Considering analyses of prior studies and the inclusion criterion metabolic syndrome, a screening failure of 30 % is expected, making screening of approximately 1100 patients necessary in order to provide the required number of patients.

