6.5.4.2 Fasting laboratory

Fasting laboratory measurements will be made at all time points specified in Table 6-1. **Fasting for 8 hours duration with water ad libitum is required prior to blood draws.** Subjects should avoid smoking within in the hours preceding the blood draws.

Fasting laboratory: Total cholesterol, triglycerides, HDL, LDL, fasting plasma glucose.

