6.5.4.3 Urinalysis

Dipsticks will be provided by the central laboratory to the study sites for local urinalysis assessments. Standard dipstick measurements for specific gravity, nitrite, protein, glucose, pH, blood, urine blood dipstick (non-hemolyzed), urine blood dipstick (hemolyzed), urobilinogen, bilirubin, ketones and WBC will be done at scheduled visits as indicated in Table 6-1. If needed conditional microscopy assessments will be optional and will be performed locally.

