

Shoelson SE, Goldfine AB (2009) Getting away from glucose: fanning the flames of obesity-induced inflammation. *Nat Med*; 15:373-4

Takahashi H, Izuka H (2012) Psoriasis and metabolic syndrome. *J Dermatol*; 39:212-8

13 **Appendix 1: Clinically notable laboratory values and vital signs**

The following criteria will be used to define expanded limits and notable abnormalities of key laboratory tests. Notable values for blood pressure and pulse are presented in section **Error! Reference source not found.**

No specific action is pre-defined within this protocol to respond to specific abnormal laboratory values except for the follow up requirement for liver events as specified in Appendix 2, as it will be decided by the investigator/qualified site staff whether and which specific action needs to be taken to respond to any abnormal values, taking into account the overall status of the subject.

Liver Function and Related Variables

| | |
|-----------------------|-----------------------------------|
| ALT (SGPT): | > 3 x Upper Limit of Normal (ULN) |
| AST (SGOT): | > 3 x ULN |
| Total bilirubin: | > 1.5 x ULN |
| Alkaline phosphatase: | > 2 x ULN |

Renal Function and Electrolyte Variables

Creatinine (serum): $> 1.5 \times \text{ULN}$

Hematology Variables

Hemoglobin: $\geq 20 \text{ g/dL}$ decrease from baseline

Platelet count: $< \text{Lower Limit of Normal (LLN)}$

White blood cell count: $< 0.8 \times \text{LLN}$

Neutrophils: $< 0.9 \times \text{LLN}$

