2.9.2 Laboratory data

The summary of laboratory evaluations will be presented for three groups of laboratory tests (hematology, clinical chemistry and urinalysis). All the laboratory parameters and biomarkers with values below and above the limit of quantification (LOQ) will be reported as LOQ/2. Descriptive summary statistics for the change from Baseline to each study visit will be presented.

These descriptive summaries will be presented by test group, laboratory test and treatment group. Change from Baseline will only be summarized for patients with both Baseline and Post-Baseline assessments.

Change from baseline = post-baseline value – baseline value

For each parameter, the maximum change from Baseline within each study period will be analyzed analogously.

Below mentioned laboratory parameters will be descriptively summarized. Frequencies and percentages will be presented for patients with clinically notable laboratory value, for below mentioned selected lab parameters:

Clinically notable laboratory values

Liver Function and Related Variables

- ALT (SGPT): $> 3 \times$ Upper Limit of Normal (ULN)
- AST (SGOT): $> 3 \times$ ULN
- Total bilirubin: $> 1.5 \times$ ULN
- Alkaline phosphatase: $> 2 \times$ ULN

Renal Function and Electrolyte Variables

- Creatinine (serum): $> 1.5 \times$ ULN

Hematology Variables

- Hemoglobin: ≥ 20 g/dL decrease from baseline
- Platelet count: $<$ Lower Limit of Normal (LLN)
- White blood cell count: $< 0.8 \times$ LLN
- Neutrophils: $< 0.9 \times$ LLN
- Eosinophils: $> 1.1 \times$ ULN
- Lymphocytes: $> 1.1 \times$ ULN

Clinically significant abnormal laboratory values will also be summarized for the following parameters of the biomarker sub-study: Adiponectin, leptin, insulin, HOMA-IR, proinsulin, IL-6, TNF-alpha, M30 assay, NT-proBNP. Only patients participating in the biomarker sub-study will be included.

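### No by-arm count against a limit is planned for low fasting glucose, urine ketones, or notable blood pressure or pulse, although the protocol raises related risks for lifestyle participants

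*SAP*

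**What the plan says.** **Risk.** Protocol 3.6 admits type 2 diabetes patients on permitted drugs because the expected benefit "which outweighs the potential small risk of hypoglycemia or ketoacidosis in the case of metformin". It also has family physicians told of participation in the programme, "so they can adequately monitor them and adjust their antidiabetic or antihypertensive medication".

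**Measurement.** Protocol 6.5.4.2 lists glucose: "Fasting laboratory: Total cholesterol, triglycerides, HDL, LDL, fasting plasma glucose". Protocol 6.5.4.3 includes ketones in the local dipstick panel: "bilirubin, ketones and WBC will be done at scheduled visits as indicated in Table 6-1". Blood pressure and pulse are taken at every scheduled visit (Protocol 6.4.6 and 6.5.2).

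**Safety analysis.** SAP 2.9.3.1 says of vital signs: "Analysis of the vital sign measurements using summary statistics for the change from Baseline for each post-baseline visit will be performed". SAP 2.9.2 says of haematology, clinical chemistry and urinalysis together: "Descriptive summary statistics for the change from Baseline to each study visit will be presented". It adds a maximum-change summary per laboratory parameter, and a table of patients with notable values for a fixed list of parameters.

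**Limits.** Appendix 1 of the protocol, whose title covers vital signs as well as laboratory values, says: "Notable values for blood pressure and pulse are presented in section". A failed cross-reference follows. No blood pressure or pulse limits appear in the protocol or SAP text supplied.

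**Other routes.** SAP 2.6.1 analyses fasting glucose and blood pressure as efficacy endpoints by MMRM. SAP 2.9.1 counts adverse events by arm, system organ class and preferred term.

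**The concern.** The protocol raises specific metabolic risks for people who change diet and activity while on glucose-lowering drugs, and the trial collects the measurements that bear on them. Harm of this kind would fall on a small subset. The natural safety question is how many patients in each arm crossed a limit, and no visible table answers it.

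Two features make a count worth having. First, glucose and blood pressure are also efficacy variables, and Protocol 3.2 treats better glucose metabolism and lower blood pressure as improvement. The main by-arm comparison of these variables is therefore one of means, which says nothing about how many patients went too low. Second, the trial is open label, and in the core study only arm B has trainers, who must relay adverse events to the investigator within 24 hours (Protocol 5.1.2). Adverse event reporting may therefore differ between arms for reasons unrelated to true frequency. Counts from measurements scheduled identically in both arms would not have that weakness.

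**Working it through.** The plan has no figure to reproduce on this point. The check is to follow each measurement through every planned output.

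**Step 1: what is collected in the core study after baseline (Table 6-1).**
- Fasting glucose: Weeks 8, 16 and 28.
- Dipstick ketones: Weeks 16 and 28.
- Blood pressure and pulse: Weeks 1, 2, 3, 4, 8, 12, 16, 20, 24 and 28.

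**Step 2: what is counted against a limit (SAP 2.9.2).** The list holds ALT, AST, total bilirubin and alkaline phosphatase (4), creatinine (1), and haemoglobin, platelets, white cells, neutrophils, eosinophils and lymphocytes (6). That is 4 + 1 + 6 = 11 parameters. None is glucose, ketones, blood pressure or pulse. SAP 2.9.2 also summarises clinically significant values for nine sub-study biomarkers, but glucose and ketones are not among them. The extension SAP (2.6.3, 2.6.4.2) repeats the eleven-parameter list and again sets no vital-sign limit.

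**Step 3: what the remaining outputs give.**

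| Output | What it shows | What it does not show |
|---|---|---|
| Change from baseline (SAP 2.9.2, 2.9.3.1; statistics defined in 2.1.1) | mean, SD, median, minimum and maximum change per visit and arm | how many patients reached a low level |
| Maximum change (SAP 2.9.2, laboratory only) | an extreme per parameter and period | direction is undefined; read as the largest signed change, it would not display falls in glucose |
| MMRM (SAP 2.6.1; glucose, blood pressure) | difference in means | any count |
| Adverse events (SAP 2.9.1) | patients by preferred term and arm | values not judged to be an event |
| Concomitant medication (SAP 2.4.3) | drugs by ATC code and arm | dose reductions |

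The minimum of the change is one patient's value at one visit. It also measures a fall, not the level reached. Raised glucose and raised systolic pressure are among the entry criteria for metabolic syndrome (Protocol 4.1), so a large fall may be the intended effect. Only a comparison with a limit separates the two.

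**Step 4: the adverse event route.** Under Protocol 7.1 an abnormal result becomes an event only if it causes symptoms, is judged clinically significant or needs therapy. That section sends investigators to Appendix 1 for alert ranges, and Appendix 1 has none for these four measurements. Relationship to the lifestyle intervention is recorded, but the related-event table in SAP 2.9.1 is worded around secukinumab, and no separate table of lifestyle-related events is described.

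**Step 5: ketones.** SAP 2.9.2 applies change from baseline to urinalysis as a group. If the dipstick result is recorded as a grade, a numeric mean change has no clear meaning.

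**The case against.** The strongest reply is that the plan is not blind to these risks. Summary statistics include the median, SD, minimum and maximum, so the most extreme change at each visit will be seen. Protocol 7.1 obliges investigators to look for clinically significant abnormal results by reviewing out-of-range values and changes from baseline. Reported hypoglycaemia, ketoacidosis or hypotension would then be counted by arm, summarised by severity and listed. The protocol calls the risk small, excludes users of insulin and sulfonylureas, and excludes type 2 diabetes with HbA1c above 8.0%. SAP 2.1.1 sends discrete variables to frequency tables, which might cover dipstick grades. The extension SAP promises a summary of clinically significant laboratory values. Protocol 9.6 and part of SAP 2.7 are not visible and could hold related analyses.

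Most of this stands, and it rules out three stronger readings. A reader might infer that these variables are reported only as mean change; SAP 2.1.1 and 2.9.1 show otherwise. A reader might infer that harm is scored as benefit. That cannot apply to ketones, where a raised result is the adverse one and which are not an efficacy endpoint. For glucose and blood pressure it is at most a side effect of comparing means, not a rule in the plan. A reader might also take low blood pressure to be a named risk; Protocol 3.6 speaks only of adjusting medication.

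What the reply does not supply is a count by arm that is independent of investigator judgement. The general rule for discrete variables leaves open how urinalysis is handled, because SAP 2.9.2 specifies change from baseline for it.

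**Conclusion.** The gap is real and small. In the visible text, no table gives the number of patients per arm with low fasting glucose, with a worsened ketone result, or with notable blood pressure or pulse. The broken reference in Appendix 1 is an error in the current text. It leaves both the investigators' alert ranges and the SAP without blood pressure and pulse limits.

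No numerical size is given. The documents state no rate of hypoglycaemia, ketoacidosis or low blood pressure, so any shift in an arm mean would rest wholly on assumed values. The consequence is confined to descriptive safety reporting; the primary analysis, alpha and sample size are untouched.

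The conclusion assumes that the redacted sections contain no such table, that the central laboratory's reference range includes a lower limit for fasting glucose, and that dipstick ketones are stored as categories.

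**What to change.** Add three descriptive tables by arm, with no testing, to SAP 2.9.2 and 2.9.3.1:

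- (a) Patients with any post-baseline fasting glucose below the central laboratory's lower limit of normal, overall and in those on glucose-lowering drugs. Define that subgroup by use at baseline so that later drug changes cannot alter it.
- (b) A shift table from baseline to worst post-baseline category of dipstick ketones, in place of numeric change from baseline.
- (c) Patients with notable blood pressure or pulse, after the sponsor's clinical team has reconciled Appendix 1 with the limits it refers to. No limit is proposed here.

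State also in SAP 2.9.2 which direction maximum change refers to.

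The cost is a short SAP revision and a few more tables from data already scheduled for collection; table (c) waits on the sponsor's limits. Three scheduled glucose samples and two dipsticks will miss episodes between visits, so the tables supplement the adverse event summaries and do not replace them.

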2.10 Patient-reported outcomes

See [Section 5.2](#)

2.11 Interim analysis

A first analysis of the core study (primary, secondary [REDACTED] endpoints related to the core study) will be performed after all subjects have completed the core study.

[REDACTED]

The two analyses will be reported in separate clinical study reports.

3 Sample size calculation

This study is primarily designed to demonstrate superiority of secukinumab combined with lifestyle intervention vs Secukinumab alone in terms of PASI90 response at week 28. A PASI90 response of 81% at week 28 under Secukinumab alone in patients with metabolic syndrome is assumed. This number is based on a retrospective analysis performed with data from the CLEAR study, taking into account the slightly higher BMI of the patient population with metabolic syndrome (BMI 23-42 kg/m², Albareda M et al., 2014) and the open-label design.

Evidence on effect size of lifestyle intervention on PASI response is relatively rare and assumptions were based on the following studies: A clinical study by [Al-Mutairi et al \(2014\)](#) showed an absolute increase of 27% in PASI75 response to biologic treatment (Infliximab, Etanercept, Ustekinumab, Adalimumab) in overweight or obese, moderate to severe psoriasis patients undergoing weight reduction compared to patients not undergoing weight reduction. However the dietary regimen used in this study was highly restrictive and consecutively led to a strong mean weight loss (-13 kg vs + 1,5 kg in the control group after 24 weeks). Naldi et al (2014) showed an absolute increase of 6% in PASI75 response to systemic treatment in overweight to obese, moderate to severe psoriasis patients undergoing diet and physical exercise compared to control patients. The lifestyle intervention in this study was less intensive and consecutively led to a smaller mean weight loss (-3kg vs -1.6 kg in the control group after 20 weeks). It seems that the extent of increase in PASI response correlates with the achieved weight loss, at least to a certain extent. PASI90 data were not available for both cited studies. The lifestyle intervention conducted in the present study is less intensive than the one applied by Al-Mutairi et al. but more intensive compared to Naldi et al. A lifestyle intervention very similar to the one applied in our study was previously able to show a mean weight loss of -3.8 kg vs. - 1.4 kg after 1 year (Kulzer B et al., 2014). Maximum weight loss can already be expected after 3-4 month. As part of the lifestyle intervention program activity tracking devices will be used in the present study to further support the lifestyle intervention.

Based on these considerations and the fact that we are looking at PASI90 response in the present study, we assume an absolute increase of 9% in PASI90 response in the Secukinumab combined with lifestyle intervention arm to 90% PASI90 responders compared to 81% PASI90 responders in the Secukinumab alone arm. An absolute increase of 9% in PASI90 responders would also be clinically meaningful.

Based on these assumptions 342 patients per arm would provide a power of 90 % at a two-sided alpha of 0.05 to demonstrate that the percentage of PASI90 responders at week 28 is higher in the Secukinumab combined with lifestyle intervention arm compared to the Secukinumab alone arm. In case the true effect size would only be 7.5 %, this sample size would still provide a power of 75 %. To compensate for some expected drop out and/or premature discontinuations, 380 patients per arm are planned to be recruited for this study.

4 Change to protocol specified analyses

Below mentioned changes to the analysis described in Section 9 of the protocol version 02 are planned.

- i. Separate analyses will be performed for subjects with fasting and non-fasting status for fasting plasma glucose, fructosamine, and HbA1c in secondary analyses
- ii. Separate analyses will be performed for subjects with fasting and non-fasting status for all the biomarkers in biomarker sub-study
- iii. Additional analysis proposed for stratification of the analysis for PASI 75, PASI 90, PASI 100 and all study biomarkers by the groups “patients achieving weight loss < 5%”, “patients achieving weight loss $\geq 5\%$ - < 10%” and “patients achieving weight loss $\geq 10\%$ ” in each treatment arm.

5 Appendix

5.1 Imputation rules

5.1.1 AE date imputation

5.1.1.1 AE end date

For the purpose of date imputation, the study treatment follow-up period date is defined as the last available visit date, i.e. including unscheduled visits after the end of study visit.

1. If the AE end date month is missing, the imputed end date should be set to the earliest of the following: study treatment follow-up period date, 31DECYYYY, date of death.
2. If the AE end date day is missing, the imputed end date should be set to the earliest of the following: study treatment follow-up period date, last day of the month, date of death.
3. If AE year is missing or AE is ongoing, the end date will not be imputed.

If the imputed AE end date is less than the existing AE start date then use AE start date as AE end date.

5.1.1.2 AE start date

AEs with completely missing onset dates will be considered to be treatment emergent. AEs with partially missing onset dates will also be included as treatment emergent when the month (if it exists) and the year occur on or later than the month and year of first administration of study treatment within this study.

Partial AE start dates are imputed with reference to the first administration of study treatment within this study as outlined in the table below.

The date value is split into day, month, year sections and referenced in the imputation table as outlined below.

	Day	Month	Year
Partial AE Start Date	Not used	MON	YYYY
Treatment Start Date	Not used	TRTM	TRTY

The following matrix explains the logic behind the imputation.

Comparison of month section	MON missing	MON<TRTM	MON=TRTM	MON>TRTM
YYYY missing	NC	NC	NC	NC
YYYY<TRTM	(D) = 01JULYYYY Before Treatment Start	(C) = 15MONYYYY Before Treatment Start	(C) = 15MONYYYY Before Treatment Start	(C) = 15MONYYYY Before Treatment Start

Comparison of month section	MON missing	MON<TRTM	MON=TRTM	MON>TRTM
YYYY=TRTY	(B) = TRTSTD+1 Uncertain	(C) = 15MONYYYY Before Treatment Start	(A) = TRTSTD+1 Uncertain	(A) = 01MONYYYY After Treatment Start
YYYY>TRTY	(E) = 01JANYYYY After Treatment Start	(A) = 01MONYYYY After Treatment Start	(A) = 01MONYYYY After Treatment Start	(A) = 01MONYYYY After Treatment Start

The following table is the legend to the logic matrix.

Relationship	
Before Treatment start	Partial date indicates AE start date prior to Treatment Start Date in this study
After Treatment start	Partial date indicates AE start date after Treatment Start Date in this study
Uncertain	Partial date insufficient to determine relationship of AE start date to Treatment Start Date in this study
Imputation calculation	
NC/Blank Uncertain	No convention
(A) After Treatment Start or Uncertain	MAX(01MONYYYY, TRTSTD+1)
(A) After Treatment Start or Uncertain	MAX(01MONYYYY, Treatment Start +1)
(C) Before Treatment Start	15MONYYYY
(D) Before Treatment Start	01JULYYYY
(E) After Treatment Start	01JANYYYY

Before imputing the AE start date, find the AE start reference date.

- If the AE end date is complete and the (imputed) AE end date < Treatment Start Date then AE start reference date = min (study informed consent date, earliest visit date).
- Else AE start reference date = Treatment Start Date

To impute AE start date:

1. If the AE start date year value is missing, the date uncertainty is too high to impute a rational date. Therefore, if the AE year value is missing, the imputed AE start date is set to NULL.
2. If the AE start date year value is less than the study treatment start date year value, the AE started before study treatment. Therefore:
 - a. If AE month is missing, the imputed AE start date is set to the mid-year point (01JULYYYY).
 - b. Else if AE month is not missing, the imputed AE start date is set to the mid-month point (15MONYYYY).
3. If the AE start date year value is greater than the study treatment start date year value, the AE started after study treatment. Therefore:
 - a. If the AE month is missing, the imputed AE start date is set to the year start point (01JANYYYY).
 - b. Else if the AE month is not missing, the imputed AE start date is set to the later of (month start point (01MONYYYY), AE start reference date + 1 day).
4. If the AE start date year value is equal to the study treatment start date year value:
 - a. And the AE month is missing the imputed AE start date is set to the AE reference start date + 1 day.
 - b. Else if the AE month is less than the study treatment start month, the imputed AE start date is set to the mid-month point (15MONYYYY).
 - c. Else if the AE month is equal to the study treatment start date month or greater than the study treatment start date month, the imputed AE start date is set to the later of (month start point (01MONYYYY), AE start reference date + 1 day).

If complete (imputed) AE end date is available and the imputed AE start date is greater than the (imputed) AE end date, then imputed AE start date should be set to the (imputed) AE end date.

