7.1 Adverse events

An adverse event (AE) is any untoward medical occurrence (e.g., any unfavorable and unintended sign [including abnormal laboratory findings], symptom or disease) in a subject or clinical investigation subject *after providing written informed consent* for participation in the study until the end of study visit. Therefore, an AE may or may not be temporally or causally associated with the use of a medicinal (investigational) product. Medical conditions/ diseases

present before first intake of study drug are only considered adverse events if they worsen after study start.

In addition, all reports of intentional misuse and abuse of the product are also considered an adverse event irrespective if a clinical event has occurred.

The occurrence of adverse events must be sought by non-directive questioning of the patient at each visit during the study. Adverse events also may be detected when they are volunteered by the patient during or between visits or through physical examination findings, laboratory test findings, or other assessments.

Abnormal laboratory values or test results constitute adverse events only if they fulfill at least one of the following criteria:

- they induce clinical signs or symptoms,
- they are considered clinically significant,
- they require therapy.

Clinically significant abnormal laboratory values or test results must be identified through a review of values outside of normal ranges/clinically notable ranges, significant changes from baseline or the previous visit, or values which are considered to be non-typical in patient with underlying disease. Investigators have the responsibility for managing the safety of individual patient and identifying adverse events. Alert ranges for laboratory and other test abnormalities are included in Appendix 1. Clinically significant abnormal laboratory values will also be assessed for the following parameters of the biomarker sub-study (only for patients participating in the biomarker sub-study): Adiponectin, leptin, insulin, HOMA-IR, proinsulin, IL-6, TNF-alpha, M30 assay, NT-proBNP.

Adverse events must be recorded in the Adverse Events CRF under the signs, symptoms or diagnosis associated with them, accompanied by the following information:

- the severity grade
 - mild: usually transient in nature and generally not interfering with normal activities
 - moderate: sufficiently discomforting to interfere with normal activities
 - severe: prevents normal activities

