2.9.1 Adverse events

Treatment emergent adverse events (events started after the first dose of secukinumab study treatment or events present prior to the first dose of secukinumab study treatment but increased in severity) will be summarized by preferred term up to 28 weeks after the first dose..

AEs will be summarized by presenting, for each treatment group, the number and percentage of patients having any AE, having an AE in each primary system organ class (SOC) and having each individual AE (preferred term).

Summaries will also be presented for AEs by severity and for secukinumab study treatment (with and without life-style intervention) related AEs. If a patient reported more than one adverse event with the same preferred term, the adverse event with the greatest severity will be presented. If a patient reported more than one adverse event within the same primary SOC, the patient will be counted only once with the greatest severity at the SOC level, where applicable. Furthermore, a listing of all adverse events, including SAE, will be provided. SAEs will be summarized.

Separate summaries will be provided for death, SAE, other significant AEs leading to secukinumab study treatment (with and without life-style intervention) discontinuation and AEs leading to dose adjustment (including secukinumab study treatment discontinuation).

Deaths occurring after signing of informed consent and prior to the start of the core study will be presented in the listing.

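### The treatment-emergent flag for missing or partial AE onset has no end-date condition, so an AE known to have ended before the first dose is counted as treatment-emergent

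*SAP*

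**What the plan says.** **Flag.** Core SAP 5.1.1.2 gives two rules. For a completely missing onset: "AEs with completely missing onset dates will be considered to be treatment emergent". For a partial onset: "AEs with partially missing onset dates will also be included as treatment emergent when the month (if it exists) and the year" fall in or after those of the first study-drug administration. Neither sentence mentions the end date, the imputed start date or the visit of report.

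**Imputation.** The same section then imputes a start date and does use the end date. "If the AE end date is complete and the (imputed) AE end date < Treatment Start Date then AE start reference date" is taken as the earlier of consent and first visit instead of the treatment start. At the end, if the imputed start lies after the end date, "then imputed AE start date should be set to the (imputed) AE end date". Where there is no year, nothing is imputed: "if the AE year value is missing, the imputed AE start date is set to NULL".

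**Definition and time limit.** SAP 2.9.1 counts "events started after the first dose of secukinumab study treatment", or events already present that became more severe. Those events "will be summarized by preferred term up to 28 weeks after the first dose".

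**Collection.** Under protocol 7.1, AEs run from written consent "for participation in the study until the end of study visit", so both the screening period and the extension are covered. Extension SAP 5.1.1.2 repeats the flag and the imputation rules.

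**The concern.** Treating an unknown onset as treatment-emergent is sensible when the timing is in doubt. A known end date before the first dose removes the doubt: the event cannot have begun or worsened after dosing. The flag counts it anyway, against the SAP's own definition. For partial onsets, one record can carry a pre-dose imputed start and a treatment-emergent flag, and the SAP does not say which governs.

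The second issue is the boundary between core and extension. The core analysis is run once all patients have completed the core study (SAP 2.11), so earlier entrants may already have extension AEs on record. In the extension, psoriasis treatment is at the physician's choice and arm A may start the lifestyle programme. An extension AE with too little onset information can reach the core table by default.

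The flag determines what is tabulated: protocol 9.5.2.1 lists non-emergent AEs but does not summarise them.

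**Working it through.** The plan gives no figure to reproduce. The check applies the written rules to test records for one assumed patient.

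**Assumed dates:** consent and earliest visit 1 March 2019; first dose 20 March 2019, which is 19 days later and within the 1-4 week screening period. Week 28 is 20 March + 196 days = 2 October 2019.

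**Rules used (SAP 5.1.1.2):**
- Flag: yes if onset is completely missing; yes if the known parts of a partial onset are not earlier than March 2019.
- Reference date: 1 March if the end date is complete and before 20 March; otherwise 20 March.
- Start, year equal to first-dose year, month missing: reference date + 1 day.
- Start, year equal and month equal or later: the later of the first of that month and reference date + 1 day.
- Start, later year, month missing: 1 January of that year.
- Cap: start not later than end date. No year: NULL.

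| Record | Flag | Imputed start | Within 28 weeks of first dose? |
|---|---|---|---|
| 1. No onset, ended 10 March 2019 | Yes | NULL | Cannot be evaluated |
| 2. No onset, ongoing or ended at Week 40 | Yes | NULL | Cannot be evaluated |
| 3. Onset March 2019, ended 10 March 2019 | Yes | 2 March 2019 | Pre-dose |
| 4. Onset 2019 only, ended 10 March 2019 | Yes | 2 March 2019 | Pre-dose |
| 5. Onset November 2019, ongoing | Yes | 1 November 2019 | No, excluded from core |
| 6. Onset 2019 only, ongoing, true onset November 2019 | Yes | 21 March 2019 | Yes, counted in core |
| 7. Onset 2020 only, ongoing | Yes | 1 January 2020 | No, excluded from core |

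**Records 1, 3 and 4** ended before the first dose, yet all are flagged. In record 3 the reference date is 1 March and the start is the later of 1 March and 2 March, so 2 March. The study day is 2 March minus 20 March = -18. If the matrix in 5.1.1.2 is followed instead of the numbered steps, the start is first dose + 1 = 21 March, and the cap pulls it back to 10 March (Day -10). Either route puts the onset before dosing, so the flag contradicts both.

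**Record 6** enters the core summary because its start becomes 20 March + 1 day. This requires Week 28 to be passed within the calendar year of the first dose: day 365 - 196 = 169, so a first dose before 18 June in a non-leap year.

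**Record 2** has no date to set against the 28-week limit, and the SAP does not say whether such an AE is kept.

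**Records 5 and 7** are handled correctly by the 28-week limit.

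**The case against.** **The section does use the end date.** A reader might infer that 5.1.1.2 ignores end dates altogether. It does not: for partial onsets they move the reference date and cap the imputed start, and record 3 is correctly imputed to before dosing. The gap is confined to the flag sentences, which refer to neither the end date nor the imputed date.

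**Extension AEs are mostly kept out.** A reader might also infer that any extension AE with an incomplete onset enters the core table. The documents do not support that. The 28-week limit removes records such as 5 and 7. For a NULL start, inclusion is undefined rather than stated. The Extension SAP (2.6.1) also splits its own reporting at Week 36 by when AEs are reported. The clear route into the core table is the year-only onset of record 6.

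**Pre-dose events may be medical history.** Protocol 7.1 treats conditions present before first drug intake as AEs only if they worsen after study start, and 6.2.4 places conditions up to the start of treatment in medical history. This reduces the number of affected records. It does not remove them: AEs are collected from consent, and SAP 5.1.1.2 itself provides for AEs that end before treatment.

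**The convention is conservative.** Counting unknown onsets errs towards over-reporting, and the same rule applies to both arms. Start and end dates are required AE items (protocol 7.1) and are subject to review and queries (8.3), so incomplete onsets should be few. This stands, and it limits the size of the problem. It does not justify counting an event known to be over before dosing.

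**Conclusion.** The point holds as a wording fault with a definite wrong result. An AE with missing onset, or partial onset in or after the first-dose month or year, is flagged treatment-emergent even when a known end date rules that out. This contradicts SAP 2.9.1 and, for partial onsets, the imputed start in the same section. The core/extension boundary is also wrong for a year-only onset in the first-dose year that truly arose in the extension, and undefined where the year is missing.

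The effect is small. It rests on some AEs having incomplete onset dates, and the documents give no count of these and no screening AE rate, so no patient number can be derived. The tables concerned are descriptive, and the primary efficacy analysis is untouched. A reader might also infer that the AE listing and table must disagree. SAP 2.9.1 promises a listing of all AEs but does not say that it shows imputed dates or is filtered by the flag, so this does not follow.

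**What to change.** In core SAP 5.1.1.2, and in the same section of the Extension SAP:

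1. State that an AE with missing or partial onset is not treatment-emergent if its complete end date is before the first dose.
2. For partial onsets with an imputed start, derive the flag from that date. This cannot serve AEs with no onset year, whose start is NULL; rules 1 and 3 cover those.
3. For AEs with no onset year, or a year-only onset in the first-dose year, assign core or extension by the visit or date of first report where the database holds it. Otherwise keep the conservative inclusion, and say so.

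The cost is a few sentences and a small change to the AE derivation. Rules 1 and 2 need no new data. Rule 3 depends on what was captured, since the AE items in protocol 7.1 do not include a reporting visit. The Extension SAP's document history places its current version after final database lock, so a change there should be recorded as post-lock.
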